10.4 Definitions of Populations to be Analyzed

10.4.1 Enrolled population

All screened participants who provide informed consent.

10.4.2 Full analysis population

All participants in the enrolled population who participated in at least one direct skin feed.

10.4.3 Per Protocol population

All participants in the full analysis population who have no major protocol violations that are determined to potentially interfere with DSFA or DMFA results. This population will serve as the primary analysis population for the DSFA and DMFA assessments.

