10.5.2 Analysis of Primary Objectives

Oocyst prevalence

The variation in the proportion of infected mosquitoes with at least one oocyst (oocyst prevalence) in DSFA and DMFA performed at two consecutive time points in the same human subject will be assessed with the per protocol population. Summary statistics will be provided for each assay and by time point (first and second). Additionally, Pearson correlation coefficients and estimates of total variation decomposed by between and within person variation will be summarized for both DSFA and DMFA. A paired t-tests will be used to evaluate the equivalence hypothesis for DSFA and DMFA. Mean differences and the corresponding 95% confidence intervals (CIs) will be provided.

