10.5.3 Analysis of Secondary Objectives

Oocyst density

The arithmetic mean oocyst density will be calculated for each subject by time point and assay. Distributions of subject-level means will be summarized by time point and assay. Medians will also be considered as a summary measure by subject. A generalized linear mixed model framework will be used

to incorporate the data from all mosquitos for each subject and summarize within and between person variability as well as summarize differences between time points. Variability and difference estimates (with 95% CIs) will be summarized for DSFA and DMFA. These analyses will be conducted on the per protocol population. A sensitivity analysis will be conducted using the full analysis population.

Sporozoite prevalence

The variation in the proportion of infected mosquitoes with at least one sporozoite in DSFA and DMFA performed at two consecutive time points in the same human subject will be assessed with the per protocol population. Summary statistics will be provided for each assay and by time point (first and second). Additionally, Pearson correlation coefficients and estimates of total variation decomposed by between and within person variation will be summarized for both DSFA and DMFA. A paired t-tests will be used to evaluate the equivalence for DSFA and DMFA. Mean differences and the corresponding 95% confidence intervals (CIs) will be provided.

Analysis of Exploratory Objectives

Oocyst and sporozoite density measured via qPCR

The arithmetic mean sporozoite and oocyst density as measured by qPCR will be calculated for each subject by time point and assay. Distributions of subject-level means will be summarized by time point and assay. Medians will also be considered as a summary measure by subject. A generalized linear mixed model framework will be used to incorporate the data from all mosquitos for each subject and summarize within and between person variability as well as summarize differences between time points. Variability and difference estimates (with 95% CIs) will be summarized for DSFA and DMFA. These analyses will be conducted on the per protocol population. A sensitivity analysis will be conducted using the full analysis population.

Assessing the relationship between oocyst and sporozoite density measured by DSFA and DMFA via microscopy and qPCR

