10.7 Timing of Analyses

Upon completion of the second DSFA and DMFA for the final participant, a topline analysis will be initiated to include the results of the primary and secondary oocyte prevalence and density results.

Following collection of the remainder of the data and database lock, all results will be described in a peer reviewed publication.

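### The primary oocyst-prevalence analysis is specified only in the per protocol set, whose exclusions are neither dated nor masked to the counts, and it lacks the full-population check given to oocyst density

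*Protocol*

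**What the plan says.** - **Analysis set.** Section 10.4.3 starts from participants with at least one direct skin feed (the full analysis population, 10.4.2) and keeps those with "no major protocol violations that are determined to potentially interfere with DSFA or DMFA results". It adds: "This population will serve as the primary analysis population for the DSFA and DMFA assessments".
- **Primary endpoint.** Under section 10.5.2, oocyst prevalence in DSFA and DMFA "will be assessed with the per protocol population". That covers the Pearson correlations, the between- and within-person variance split and the test: "A paired t-tests will be used to evaluate the equivalence hypothesis for DSFA and DMFA". No second analysis set is named.
- **Other endpoints.** Section 10.5.3 says for oocyst density: "A sensitivity analysis will be conducted using the full analysis population". The same sentence follows the qPCR densities and the DSFA–DMFA relationship. It does not follow sporozoite prevalence.
- **Timing.** Section 10.5 requires the SAP before database lock. Section 10.7 says: "Upon completion of the second DSFA and DMFA for the final participant, a topline analysis will be initiated". It covers the oocyst prevalence and density results. The remaining data and database lock come afterwards.
- **Deviations.** Under section 9.5.6 the PI or a sub-investigator grades each deviation as major or minor. Major deviations go to the review boards within 48 hours of awareness.

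**The concern.** The study asks whether two feeds on the same person agree, and section 10.3 intends the correlation between feeds to inform the follow-on design. A participant whose two feeds differ sharply invites a closer look for something that went wrong. If that look happens with the counts in view, and the decision that a violation could have interfered is made then, the pairs lost will tend to be discordant ones. Losing them shrinks the SD of the differences, raises the correlation, lowers the estimated within-person variance and makes equivalence easier to declare.

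A full-population run would show whether exclusions drove the result. The protocol provides that run for a secondary endpoint and the exploratory ones, but not for the primary.

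**Working it through.** **Inputs**
- 36 pairs and 25 mosquitoes per feed; counts Bin(25, p) with p from Beta(1.5, 6); margin ±7 points (section 10.3). Section 10.2 fixes no margin, so 7 points is taken from the power statement.
- 0.025 per side. This is an assumption drawn from the 95% confidence interval in 10.5.2; no alpha is stated.
- Number of exclusions: not given. One to three are shown as an assumption.

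**SD of the paired difference**
- Mean of p = 1.5/7.5 = 0.20. Var(p) = 1.5 × 6/(7.5² × 8.5) = 0.01882.
- Binomial part: (0.20 × 0.80 − 0.01882)/25 = 0.00565.
- Constant probability: SD = √(2 × 0.00565) = 0.106.
- Independent days: SD = √(2 × (0.01882 + 0.00565)) = 0.221.

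**The protocol's own figures**

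Equivalence is declared when mean ± t × SD/√36 lies inside ±0.07. Simulation gives 4.4–4.5% for independent days (stated 4%) and about 93.5% for constant probability (stated 90%). At 0.05 per side the figures are about 19% and 97%, so 0.025 per side fits better. The 90% is not reproduced exactly, but it does not bear on this point.

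**False equivalence when the true difference equals the margin**

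Pairs share an underlying probability and day 2 is 7 points higher on average. Two shapes of shift were tried: 0.07 added to every probability, and day 2 drawn at the same quantile of a Beta with mean 0.27 and the same precision. The k pairs with the largest absolute difference are then removed.

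| Pairs lost | Additive shift | Quantile shift |
|---|---|---|
| 0 | 2.6% | 2.7% |
| 1 | 5.8% | 6.6% |
| 2 | 10.2% | 12.0% |
| 3 | 15.9% | 18.6% |

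With one to three pairs removed at random, the rate stays between 2.5% and 2.8% under both shapes. These figures are worst case as to which pairs are lost, but they still depend on the shape of the shift. A proportional rise (day 2 probability 1.35 times day 1) gives 3.1%, 8.3%, 15.4% and 24.3%.

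**Pass rate when the true difference is zero**

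| Pairs lost | Independent days, most discordant | Independent days, random | Constant p, most discordant | Constant p, random |
|---|---|---|---|---|
| 0 | 4.4% | 4.4% | 93.6% | 93.6% |
| 1 | 9.5% | 3.8% | 96.8% | 92.8% |
| 2 | 14.8% | 3.3% | 98.2% | 91.8% |
| 3 | 20.7% | 2.8% | 98.9% | 90.8% |

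**Spread**

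For independent days the SD falls from 0.221 to 0.204, 0.191 and 0.179, which is 8%, 14% and 19% lower. The variance components and correlation would shift in the same direction.

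**Timing**

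Oocysts are read on day 9 or 10 after each feed (sections 8.1.5 and 8.1.9.3), and topline precedes lock (10.7). Nothing dates the interference determination before either event.

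**The case against.** The case on the other side has substance.

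- **Exclusion needs a major violation.** A reader might infer that pairs can be dropped on a judgement about the assay results themselves. Section 10.4.3 does not say that: a discordant pair without a major violation stays in. If violations are unrelated to discordance and only the most discordant of 2, 3 or 4 violators is dropped, the independent-days pass rate is 4.4%, 4.8% or 5.1%, against 4.4% with all pairs kept. This stands, and it makes the worst-case figures a ceiling on selection, not a forecast.
- **The rise from 4.4% to about 21% is not false equivalence.** A reader might take it so. In that scenario both days share one distribution, the true mean difference is zero and equivalence is true. The error rate has to be read at the margin.
- **Deviations are reported early.** A violation noticed at the feed would normally be reported as major before its oocysts are read, and section 10.5 puts all data in listings. This stands for violations noticed promptly. It does not date the separate interference determination or cover violations found late.
- **The SAP may settle this.** Exclusion listings commonly sit there. But the SAP is due only before lock, which comes after topline starts, and the protocol itself says which endpoints get the full-population run.
- **The contrast may be deliberate.** Mixed models for density can use participants with one feed and a paired t-test cannot. The protocol gives no such reason, and participants with both feeds who were excluded could still be analysed. Since withdrawn participants are replaced, the extra run may add few pairs.
- **A per protocol primary set is usual for equivalence.** Agreed; nothing here argues for replacing it.

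**Conclusion.** The point holds as a minor one. The primary analysis has a single population, entry to that population turns on an undated and unmasked determination, and the schedule allows the determination to follow the counts. The documents do not show that it will, nor that discordant pairs will be removed.

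The size is conditional. If the 1, 2 or 3 most discordant of 36 pairs were the ones lost, false equivalence at a true 7-point difference would rise from about 2.5% to about 6–7%, 10–12% and 16–19%. This assumes 0.025 per side, a ±7-point margin, constant-probability pairs and an additive or quantile shift. Exclusions unrelated to discordance leave that error rate unchanged and slightly lower the pass rate when the true difference is zero. The model is the protocol's model for DSFA; it gives none for DMFA, so no size is claimed there.

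**What to change.** - **Section 10.4.3:** require the list of per protocol exclusions, with reasons, to be finalised without reference to oocyst counts and before the topline analysis starts.
- **Section 10.5.2, and sporozoite prevalence in 10.5.3:** add the full analysis population sensitivity sentence already used for oocyst density, applied to participants with both feeds and covering the equivalence test, correlation and variance components.

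The per protocol set stays primary and no new decision rule is needed. The cost is a few sentences, one or two extra tables, and the need to explain any discrepancy between the sets.

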10.2 Statistical Hypothesis

We are interested in assessing the equivalence of oocyst prevalence measured in the same subject undergoing DSFA at two consecutive 24-hour time periods. If the difference in oocyst prevalence measured on two consecutive days is represented as Δ , the null (H_0) and alternative (H_1) hypotheses of the primary efficacy endpoint analysis are as follows:

$$H_0: \Delta > \Delta_E \text{ or } \Delta < -\Delta_E$$

$$H_1: -\Delta_E < \Delta < \Delta_E$$

Where Δ_E represents a value such that range that would support the use of a “before-after” trial design in a future mAb study.

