[figure not shown]

With these limitations in mind a simulation approach was used to understand the power to reject various equivalence null hypotheses ($-\Delta_E, \Delta_E$) assuming either high correlation within subjects for consecutive DSFA or independence between measurements.

Briefly, we assume that the number of positive mosquitos for any DSFA is binomially distributed $x_{it} \sim \text{Bin}(25, p_{it})$ where $p_{it} \sim \text{Beta}(1.5, 6)$. The parameters for the Beta distribution were selected to generate a distribution of positive mosquitos which achieves, approximately, the characteristics listed in points 3 and 4 above (16% with 0 positive mosquitos and 50% less than 5). For a single draw of $x_t = x_{1t}, \dots, x_{36t}$, the distribution of mosquitos looks similar to the data observed above.

[figure not shown]
We considered two scenarios in our simulations. First, we assume that observations within person on consecutive days are independent. That is, $x_{i1} \sim \text{Bin}(25, p_{i1})$ and $x_{i2} \sim \text{Bin}(25, p_{i2})$ where p_{i1} and p_{i2} are independent draws from the Beta distribution. Second, we assume the underlying transmission probability within a person is constant for the two consecutive feeds and $x_{i1} \sim \text{Bin}(25, p_i)$ and $x_{i2} \sim \text{Bin}(25, p_i)$ where $p_i = p_{i1} = p_{i2}$. A simulated example for these two scenarios is shown in the figure below.

Figure 11. Simulating scenarios with independent daily transmission probabilities within subjects (left) or constant transmission probabilities over 24 hours within subjects (right).

[figure not shown]
We simulated this experiment based on both of the scenarios and then used a paired t-test to test for equivalence in oocyst prevalence at various equivalence intervals ($-\Delta_E, \Delta_E$). We find that with the current sample size of 36 subjects and 25 mosquitos per feeding assay, we will have 90% power to reject the null hypothesis that the difference of oocyst prevalence between consecutive feeding assays is greater than $+\/-7\%$ for correlated data (scenario 2). However, the same equivalence interval ($\Delta_E=0.07$) has only 4% power assuming independent data (scenario 1). Power for the equivalence test over a range of equivalence intervals and both scenarios are shown in the figure below.

Figure 12. Power calculation for equivalence test

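### One per protocol set serves both assays, so a violation judged to affect only DSFA or only DMFA also removes a valid pair from the other assay's analysis; the cost is probably small

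*Protocol*

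**What the plan says.** Section 10.4.3 takes the full analysis population and keeps participants with "no major protocol violations that are determined to potentially interfere with DSFA or DMFA results". It adds: "This population will serve as the primary analysis population for the DSFA and DMFA assessments". There is one set, its unit is the participant, and interference with either assay is enough for exclusion.

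Section 10.2 states the hypothesis for the skin feed alone, as "assessing the equivalence of oocyst prevalence measured in the same subject undergoing DSFA at two consecutive 24-hour time periods". Section 10.5.2 says that variation in prevalence in feeds "performed at two consecutive time points in the same human subject will be assessed with the per protocol population", and that "A paired t-tests will be used to evaluate the equivalence hypothesis for DSFA and DMFA". Section 5.2.1 also makes differences in prevalence between the two assays part of the primary endpoint.

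Section 8.1.5 describes separate procedures. DMFA uses 0.12 mL of drawn blood in warmed glass feeders, with two cups of 30 mosquitoes. DSFA uses one cup of 60 placed on the calf or arm for 15 minutes.

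**The concern.** Because the procedures differ, a major violation can compromise one assay and leave the other sound. A blood sample for the membrane feed that was handled against the protocol is an example: it need not say anything about that person's skin feeds. Once such a violation is judged to interfere with DMFA, section 10.4.3 removes the whole person, and the valid DSFA pair goes too. For the DSFA test this loses information, and it removes no DSFA error in return. A violation confined to the skin feed costs the DMFA analysis a valid pair in the same way.

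What is at stake is precision and power in a study of about 36 to 45 pairs, chiefly for the DSFA equivalence test.

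**Working it through.** **Does any other text bring the pair back?**

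- Section 10.5.2 assigns the prevalence analysis to the per protocol set and names no full-analysis sensitivity analysis. Section 10.5.3 names one for oocyst density and for the exploratory analyses.
- Section 10.6 uses observed data within the relevant study population, so data from a person outside that population stay out.
- Section 6.3.4 replaces participants who are withdrawn or terminated. Someone who completed every procedure, one of them in violation, is neither.

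Nothing limits an exclusion to the affected assay.

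**Inputs for the size of the loss.** Section 10.3 gives the model: prevalence p from Beta(1.5, 6), positives from Bin(25, p), and p either the same on both days (scenario 2) or drawn independently (scenario 1). It uses 36 subjects and a margin of 0.07. The protocol does not state the level of the equivalence test. Section 10.5.2 says "Mean differences and the corresponding 95% confidence intervals (CIs) will be provided", so the rule taken here is that the 95% interval lies inside ±0.07, that is, 2.5% per side.

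**Standard deviation of the paired difference.**

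- E[p(1−p)] = (1.5 × 6)/(7.5 × 8.5) = 0.1412.
- Scenario 2: √(2 × 0.1412/25) = 0.1063.
- Scenario 1 adds 2 × Var(p), with Var(p) = 9/(7.5² × 8.5) = 0.0188: √(0.0113 + 0.0376) = 0.221.

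**The plan's own figures.** Section 10.3 says that "with the current sample size of 36 subjects and 25 mosquitos per feeding assay, we will have 90% power to reject the null hypothesis" in scenario 2, against 4% in scenario 1. Simulating the paired t equivalence test (40,000 to 100,000 runs) gives:

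| Level per side | Scenario 2 | Scenario 1 |
|---|---|---|
| 2.5% | 93.5% | 4.4% to 4.6% |
| 5% | 97% | 19% |

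The 4% reproduces at 2.5% per side, which supports the 95% interval rule. The 90% does not reproduce exactly: the computed value is 3.5 points higher, so the stated figure is on the cautious side.

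**Effect of losing DSFA pairs to DMFA-only violations** (scenario 2, 2.5% per side, pairs lost at random; the number lost is an assumption):

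| Pairs lost from 36 | Pairs left | Power |
|---|---|---|
| 0 | 36 | 93.5% |
| 1 | 35 | 92.6% |
| 2 | 34 | 91.7% |
| 3 | 33 | 90.7% |
| 4 | 32 | 89.4% |
| 6 | 30 | 86.7% |

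The average loss over the first four pairs is (93.5 − 89.4)/4 = 1.0 point per pair. The mean half-width of the 95% interval goes from 3.6 percentage points at 36 pairs to 3.7 at 34, 3.8 at 32 and 3.9 at 30.

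**Starting from the enrolment target.** Section 6.3.2 aims for about 45 gametocytemic participants. At 45 pairs the same model gives 97.9%, at 41 it gives 96.7% and at 38 it gives 94.9%. Losing 45 − 36 = 9 pairs only brings power back to 93.5%.

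**The case against.** The strongest argument for one set is comparability. Section 5.2.1 puts DSFA-versus-DMFA differences in prevalence inside the primary endpoint, and a common set means that both summaries and their difference describe the same people. This stands for the between-assay comparisons, and the fix must respect it. It does not extend to the within-assay tests of day 1 against day 2, which need validity on one assay only.

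Three arguments limit how often the rule would bite, and all have force:

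- Exclusion needs a major violation and a case-by-case judgement that it interferes. A feeder failure that yields no DMFA result may simply be missing data under section 10.6, with the DSFA pair kept.
- Many conceivable violations would affect both assays: recent antimalarial use, a missed 24-hour window, or faults in mosquito rearing or holding.
- Sections 6.3.2 and 6.3.4 continue screening until the target number have undergone all procedures. A person whose DMFA was not done may not count towards it. This does not clearly cover a DMFA that was done but done wrongly.

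It can also be said that the statistical analysis plan may settle the matter. Section 10.5 does leave detailed methods to that plan. However, section 10.4.3 itself fixes a joint set and its use, so assay-specific sets would depart from the protocol as written.

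A reader might infer that the DSFA test is materially underpowered, or that the joint set biases it. The documents support neither. They give no violation rate, and power stays above the stated 90% until four of 36 pairs are lost. Nor do they show that DMFA-only violations are related to day-to-day change in skin-feed prevalence.

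**Conclusion.** The point holds as a matter of definition. One participant-level set, triggered by either assay, is primary for both, and it discards valid pairs whenever a violation is confined to one assay.

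The size is probably small: about 1 point of power and a few hundredths to a tenth of a percentage point of interval half-width per pair, starting from 36 pairs. There is more slack if about 45 complete. The protocol does not say that the excess over 36 is meant to cover violations, and the figure that sets out the sample size is not shown.

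These figures rest on the constant-probability scenario, 25 mosquitoes per feed, the 0.07 margin, the 95% interval rule and random loss. The number of pairs lost is assumed. The gap between 93.5% and the stated 90% does not bear on the conclusion. The change is optional but worth making because it costs so little.

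**What to change.** Amend section 10.4.3 to define per protocol status by assay, with the determination made before the assay results are reviewed:

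- Within-DSFA analyses use participants without a major violation that could interfere with DSFA.
- Within-DMFA analyses use participants without a major violation that could interfere with DMFA.
- Every DSFA-versus-DMFA comparison uses participants valid on both. This covers the between-assay prevalence differences in section 5.2.1 as well as the comparisons in section 10.5.3.

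The cost is a sentence or two in section 10.4.3 and a field in the deviation log showing which assay is affected. Denominators may differ slightly between the DSFA and DMFA tables, so each table should state its own.

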10.5 Analysis Methodology

All statistical methods shall be detailed in a statistical analysis plan (SAP) that will be finalized prior to database lock.

The number of subjects enrolled and having undergone DSFA will be summarized. Demographic data will be summarized by descriptive statistics. Except where otherwise indicated in this document or the SAP, summary statistics will be composed of the mean, standard deviation, 1st, 2nd, and 3rd quartile, and the minimum and maximum for continuous variables. For categorical variables, the count and proportion (using one digit beyond the decimal point) will be presented. Correlation coefficients will be used to summarize associations between measurements. Scatter plots and Bland-Altman plots will be used to graphically explore relationships between measurements. All study data will be presented in listings.

A full description of analyses will be described in the SAP, but brief descriptions have been provided in the subsequent sub-sections.

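### The SAP deadline in 10.5 falls after the topline primary analysis in 10.7, so the unstated equivalence margin and test level could be set with the primary result in hand

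*Protocol*

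**What the plan says.** - **Margin.** Protocol 10.2 states null and alternative hypotheses for equivalence of DSFA oocyst prevalence across two consecutive days. Delta_E "represents a value such that range that would support the use of a" before-after design. That is a purpose, not a number.
- **Power.** In 10.3 the simulation "used a paired t-test to test for equivalence in oocyst prevalence at various equivalence intervals". For the margin of 0.07 it reports that "we will have 90% power to reject the null hypothesis that the difference of oocyst prevalence between consecutive feeding assays is greater than" that margin if the transmission probability is constant within a person, and 4% power if the feeds are independent. Both figures apply "with the current sample size of 36 subjects and 25 mosquitos per feeding assay". Power at other margins is in Figure 12, which is not reproduced in the text at hand.
- **Test.** 10.5.2 says "A paired t-tests will be used to evaluate the equivalence hypothesis for DSFA and DMFA" and "Mean differences and the corresponding 95% confidence intervals (CIs) will be provided". It gives no alpha and does not make the interval the decision rule.
- **Deadline for methods.** 10.5: "All statistical methods shall be detailed in a statistical analysis plan (SAP) that will be finalized prior to database lock".
- **Order of analyses.** 10.7: "Upon completion of the second DSFA and DMFA for the final participant, a topline analysis will be initiated". This topline includes the primary prevalence result. Collection of the remaining data and database lock come in the next sentence, after it.

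**The concern.** Leaving a margin and a test level to the SAP is ordinary practice and would not be worth raising alone. The problem is the order that the protocol fixes. The last date for the SAP is database lock, and the primary result is produced before lock. A team could follow both sections to the letter, see the mean DSFA difference and its interval, and then write down Delta_E and the confidence level. No section closes that route. The study has a single group, and the protocol describes no masking of feeding results.

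An equivalence test has controlled error only if its margin is fixed independently of the data. Sections 5.1 and 10.3 say the results bear on whether a before-after design can be used in the Phase 2b trial. A statement that equivalence was shown would carry little weight there if the margin could have followed the result.

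**Working it through.** **Inputs.** All are from Protocol 10.3: n = 36 subjects; 25 mosquitoes per feed; count ~ Bin(25, p); p ~ Beta(1.5, 6). In scenario 1, p is drawn independently for each day. In scenario 2, p is constant within a person. Stated power at margin 0.07 is 90% (scenario 2) and 4% (scenario 1). The test level is not stated, so two rules were tried: the 95% CI inside the margin (0.025 per side) and the 90% CI inside the margin (0.05 per side).

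**Step 1: standard error of the mean paired difference.**
- E[p(1−p)] = (1.5 × 6)/(7.5 × 8.5) = 0.1412. Divided by 25, this gives a binomial variance of 0.00565.
- Var(p) = 0.2 × 0.8/8.5 = 0.01882.
- Scenario 2: SD = √(2 × 0.00565) = 0.106; SE = 0.106/6 = 0.0177.
- Scenario 1: SD = √(2 × (0.00565 + 0.01882)) = 0.221; SE = 0.221/6 = 0.0369.

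**Step 2: pass rule.** Equivalence is declared if |mean difference| + t × SE < Delta_E, with t on 35 df = 2.030 (95% CI) or 1.690 (90% CI). With a true mean difference of zero, the pass probability is roughly 2Φ(Delta_E/SE − t) − 1. For scenario 1 at 0.10 with the 95% CI rule: 0.10/0.0369 − 2.030 ≈ 0.68, which gives about 50%. This approximation fails when Delta_E/SE is close to or below t, as in scenario 1 at 0.07 with the 95% CI (0.07/0.0369 = 1.90 < 2.03), because it ignores sampling variation in the SE. The table is therefore from simulation (100,000 trials per scenario).

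**Step 3: the protocol's own figures at margin 0.07.**

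| Rule | Constant p (stated 90%) | Independent (stated 4%) |
|---|---|---|
| 95% CI | about 94% | about 4% |
| 90% CI | about 97% | about 19% |

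The 95% CI rule is the closest match. It agrees with the 4% but lies nearly 4 points above the stated 90%. None of the levels tried (0.05 down to 0.005 per side) gives both figures, so the level can be inferred from the power text but not read off it.

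**Step 4: dependence on the two open choices, independent feeds.**

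| Rule | ±0.05 | ±0.07 | ±0.10 | ±0.12 | ±0.15 |
|---|---|---|---|---|---|
| 95% CI | 0.02% | 4% | 50% | 77% | 95% |
| 90% CI | 0.5% | 19% | 69% | 88% | 98% |

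The median smallest margin that would just pass under the 95% CI rule is 0.048 with constant p and 0.100 with independent feeds. Both are values that someone looking for a plausible margin might consider.

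**Step 5: the order of events.** 10.2 and 10.5.2 leave margin and level open. 10.5 closes them at lock at the latest. 10.7 puts the primary result before lock. The interval between topline and lock is where the choice could follow the data.

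**The case against.** **The database-lock date is only a latest date.** The SAP may be signed well before topline, and nothing says the margin will still be open then. This stands. The text permits a choice after the result; it does not show that one is planned. But a deadline should exclude the problem, and this one does not.

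**A margin is already given.** A reader might take 0.07 as the margin and 95% as the level. The documents do not support that. The 0.07 is one of several intervals used for power, and the 95% CI is a reporting item. Nor should 0.07 be imposed on the ground that power is quoted only there, because 10.3 refers to a figure with power over a range of margins.

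**The pass probabilities are not error rates.** This is correct. In scenario 1 both days share one Beta distribution, so the true mean difference is zero and the alternative in 10.2 is true. A reader might treat the 4% as protection against a wrong conclusion, lost under a 90% CI. The protocol calls it power, and it is power. The figures measure how far the verdict depends on the open choices, and no more.

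**The study mainly estimates variability.** 10.5.2 also reports correlations, variance components and mean differences with intervals, none of which depends on Delta_E, and no section ties the Phase 2b decision to passing the test. This limits the damage. It does not rescue the formal hypothesis test.

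**Topline starts too early.** One might infer that topline runs before the last oocysts are read on day 9 or 10 after feeding. 10.7 says only that it is initiated at the last feed, so this is loose wording and not a source of bias.

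**Conclusion.** The point holds as a fault of sequence. Sections 10.2, 10.5, 10.5.2 and 10.7 together allow the equivalence margin and test level to be set after the primary result is known. Under the protocol's model with independent feeds, the probability of declaring equivalence goes from about 4% to 50% to 77% as the margin goes from 0.07 to 0.10 to 0.12 under a 95% CI rule. At 0.07 it goes from about 4% to about 19% if the rule becomes a 90% CI.

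These figures rest on n = 36, 25 mosquitoes per feed, Beta(1.5, 6) and a true mean difference of zero. The size of any type I error inflation cannot be calculated, because it would depend on how the margin was chosen. The documents do not show an intention to choose late, and they do not make deferral to the SAP wrong in itself.

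**What to change.** 1. **10.5:** replace the database-lock deadline with a requirement that the SAP be final before any topline or interim summary of feeding-assay results.
2. **10.2 or the SAP, by that date:** fix a numeric Delta_E with its scientific justification, and the decision rule, namely whether the 90% or the 95% CI of the mean difference must lie within ±Delta_E. A margin of 0.07 with a 95% CI would be consistent with the power text, but the choice is for the sponsor to justify.
3. **10.7:** state that topline is run on a cleaned and locked oocyst dataset after the last day 9/10 read.

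The cost is protocol wording, an earlier SAP sign-off and a topline start about 10 days later. No change to sample size, visits or assays is needed.
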